3.1 General Design

This study is a pilot cross-sectional study.

Study Schema:

Any patient with a familial syndrome at risk of kidney cancer (VHL, BHD, HLRCC or TSC) undergoing annual imaging screening is eligible, but we will target inclusion of at least 10 subjects who have at least 1 kidney lesion. Therefore, up to 5 subjects may have no current kidney lesions. Subject participation will be

only for the day of CEUS study. There will be no follow-up period for this study. However, if results are encouraging, a longitudinal observational study may follow, and these same subjects would be eligible for enrollment.

Abdominal imaging in patients with VHL is also used to monitor the pancreas. Although pancreatic lesions are less common than kidney lesions, cross-sectional imaging allows for monitoring of both organs. For patients with VHL, we will image the pancreas in addition the kidneys in order to establish parameters for pancreas CEUS. CEUS of the pancreas is not novel⁵¹, but its use for screening in patients at risk of pancreas lesions has not been investigated.

Following completion of imaging, all CEUS, MRI (within 4 months) and B-mode (at time of CEUS) US studies will be de-identified. Blinded radiologists will interpret images and provide an overall assessment of risk of malignancy to each kidney using the Bosniak criteria for each kidney lesion present. The Bosniak criteria places cystic lesions into one of 5 categories (I, II, IIF, III and IV) based on lesion characteristics. CEUS based diagnosis will be compared to the diagnoses on routine B-mode US and contrast-enhanced MRI.

3.2 Primary Study Endpoints

The primary study endpoint will be agreement of qualitative radiologist review of CEUS images with routine B-mode US.

3.3 Secondary Study Endpoints

The secondary study endpoint will be agreement of qualitative radiologist review of CEUS images with contrast-enhanced MRI.

3.4 Primary Safety Endpoints

- Adverse effects of microbubble contrast administration.
- Development of hematuria post-CEUS.

4 Subject Selection and Withdrawal

4.1 Inclusion Criteria

To be eligible for the present study, patients must meet the following criteria:

4.1.1 Able to provide written informed consent 

4.1.2 Willing to comply with protocol requirements 

4.1.3 At least 18 years of age

4.1.4 Carry a diagnosis of VHL, BHD, HLRCC or TSC and able to undergo routine clinical screening tests for RCC

4.2 Exclusion Criteria

4.2.1 Critically ill or medically unstable or in an intensive care setting and whose critical course during the observation period would be unpredictable

4.2.2 Known hypersensitivity to sulfur hexafluoride or to any component of perflutren lipid (Definity®) or sulfur hexafluoride (Lumason®)

4.2.3 Right to left shunt, severe pulmonary hypertension (Pulmonary artery pressure >90mmHg), or adult respiratory distress syndrome

4.2.4 Active cardiac disease including any of the following:

- Severe congestive heart failure (class IV in accordance with the classification of the New York Heart Association)
- Unstable angina.
- Symptomatic arrhythmia (i.e. tachycardia, bradycardia, supraventricular tachycardia, ventricular fibrillation, ventricular tachycardia, atrial flutter or fibrillation).
- Myocardial infarction within 14 days prior to the date of proposed microbubble administration.

4.2.5 Has any other medical condition or other circumstances that would significantly decrease the chances of obtaining reliable data or of achieving the study objectives such as: [REDACTED]

- Mental illness
- Drug abuse

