Associated Toxicities

Most safety studies have been performed in cardiac patients as this was the only FDA approved indication until April 4, 2016 when Lumason® was approved for liver applications. Thus far, microbubble agents have been shown to be quite safe^{12,13}. In pre-market clinical trials, 1716 subjects were evaluated with activated perflutren lipid. Of the 1716 subjects, 144 (8.4%) had at least one treatment-related adverse reaction. There were 26 serious adverse events and 15 (0.9%) subjects discontinued because of an adverse event, 1 due to a hypersensitivity reaction and the rest due to dizziness, chest pain, dyspnea or back pain. The events appeared within 1 – 15 minutes of the drug administration and were of moderate intensity resolving usually without treatment within minutes or hours after onset. Of the 11 other serious adverse events, which appeared within 2-15 days of the drug administration, all appeared to be a progression of underlying cardiac and non-cardiac disease. Nineteen subjects (1.1%) suffered serious cardiopulmonary adverse events including 8 deaths. The deaths occurred several days after activated perflutren lipid administration and appear to be related to the course of underlying disease.

For all AEs, there were no differences in the overall incidence based on age, gender, or route of administration. The most common events were (% of patients experiencing): headache (2.3%), back and renal pain (1.2%), flushing (1.1%) and nausea (1.0%).

Initial post-marketing experience, which included over 1 million patients with 5 years surveillance, showed the only medically significant risk was rare allergic events, occurring at a rate of 1 in 10,000¹³.

Cardiopulmonary Reactions^[14]

Cardiopulmonary contraindications include cardiac shunts and hypersensitivity to perflutren. The initial mandated 30-minute monitoring period was limited to patients with pulmonary hypertension or unstable cardiopulmonary conditions. The mandatory 30-minute monitoring period was removed in 2011, although a statement remained that most serious cardiopulmonary reactions occur within 30 minutes of administration. For this reason, the label states that cardiopulmonary resuscitation personnel and equipment be readily available prior to perflutren administration, and that all patients be monitored for acute reactions.

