Although recent studies have shown no increased risk in patients with pulmonary hypertension¹⁴, patients with a history of known cardiac shunts, pulmonary hypertension or unstable cardiopulmonary conditions

will be excluded from our study. In addition, any patient with a suspected reaction during imaging will be monitored 30-minutes post-contrast agent administration by clinical or research nurse.

Hypersensitivity Reactions

Anaphylaxis to perflutren is extremely rare, however, in case of a severe reaction, EpiPen® (epinephrine) injections will be kept near the US machine for all patients.

High Ultrasound Mechanical Index (MI)

While high ultrasound MI of the heart may cause microbubble cavitation and subsequent ventricular arrhythmias, this was seen only at MI>1.6, higher than the typical MI used for microbubble disruption, with an agent no longer in clinical use.¹⁵ No premature ventricular contractions were seen with MI≤1.1. Large clinical trials using MI≤1.0 for expanded cardiac indications have shown no significant concerns for arrhythmias^{13,16,17,13,16,17}

Nevertheless, the safety of perflutren at MIs >0.8 has not yet been established by the manufacturer. However, real-time measurement of renal blood flow in 19 healthy subjects using perflutren was reported, using a flash replenishment high-MI (MI of 1.0) US technique. The contrast agent was well tolerated with no serious adverse events. One patient each had a 20mmHg increase in systolic blood pressure, a very brief and mild episode of flushing, and mild back pain, but no cardiac arrhythmias were recorded during the study period¹⁸. A second study using Sonovue® contrast agent with flash-replenishment high-MI to detect changes in kidney perfusion via US in 10 normal volunteers reported the agent was well tolerated, and not associated with any adverse events¹⁹.

Small pre-clinical studies performed in rodents and pigs²⁰⁻²³ showed conflicting results. One group showed glomerular capillary hemorrhage in exposed animals while other groups showed no sign of damage. The clinical relevance of these findings has not yet been investigated and is believed to be minimal, if any.

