4.2.6 Female patient who is pregnant or lactating

4.2.7 Obesity that limits obtainment of acceptable images

4.3 Subject Recruitment and Screening

Subjects will be recruited from the UNC von Hippel-Lindau Clinical Care Center, under the directorship of [name], NP and [name]. UNC currently has 20-25 patients who undergo annual screening. No specific handouts will be used as the target population is very specific. Principal investigator and sub-investigators will approach patients that meet inclusion and exclusion criteria to determine interest in participation. There are no laboratory tests required. Prior imaging to determine if any lesions are present (as we are targeting at least 10 subjects who have at least one lesion) will be required.

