7.1 Sample Size Determination

The goal of this feasibility study is to enroll a total of 15 subjects with familial syndrome at risk of kidney cancer, with at least 10 having 1 kidney lesion. This will yield up to 30 kidneys which will be assessed using CEUS, B-mode US and contrast MRI. Each of the 3 images on each kidney read by 3 readers with a Bosniak score assigned to each lesion. The primary objective is to assess agreement between the new imaging approach via CEUS with the most widely used existing technique, contrast-enhanced MRI, based on dichotomized Bosniak scores (I/II/IIF versus III/IV). A high kappa would warrant further investigation of CEUS as an alternative to MRI and other approaches. As described below in section 7.2, overall point estimates and confidence intervals will be computed for the kappa of interest based on averaging across the 3 readers. The proposed sample size will yield 95% confidence intervals with widths no greater than 0.30 over a wide range of true kappas, which should provide sufficient precision in kappa estimates to make a determination regarding feasibility of CEUS for future research.

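### Section 1.2 excludes any known cardiac shunt or pulmonary hypertension, but criterion 4.2.3 excludes only right-to-left shunt and pulmonary artery pressure above 90 mmHg

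*Combined protocol and SAP*

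**What the plan says.** Section 1.2 (Investigational Agent, under Cardiopulmonary Reactions) gives the safety background and then makes a commitment about this study: "patients with a history of known cardiac shunts, pulmonary hypertension or unstable cardiopulmonary conditions" "will be excluded from our study". It states no shunt direction and no pressure threshold. Just before this, the same section says "Cardiopulmonary contraindications include cardiac shunts and hypersensitivity to perflutren", again with no direction.

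Section 4.2 is the eligibility list. Criterion 4.2.3 reads "Right to left shunt, severe pulmonary hypertension (Pulmonary artery pressure >90mmHg), or adult respiratory distress syndrome".

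On how the list is used, Section 4.3 says "Principal investigator and sub-investigators will approach patients that meet inclusion and exclusion criteria to determine interest in participation". Section 5.3 also ties selection to the criteria, and the Study Procedures Table in Appendix 1 places the inclusion/exclusion check at screening.

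**The concern.** Both statements are current protocol text, and the Section 1.2 sentence is a rule for this study rather than a summary of literature. If the two differ, a candidate's eligibility for contrast depends on which page the investigator consults. Someone working from Section 4 alone could enrol a patient whom the safety section says is excluded. Someone applying Section 1.2 would turn away a patient who passes every listed criterion. In either case it would be unclear whether a deviation had occurred.

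The shunt half carries more weight, because Section 1.2 itself names cardiac shunts as a contraindication. The pulmonary-hypertension half is weaker. Section 1.2 reports that "recent studies have shown no increased risk in patients with pulmonary hypertension", does not list the condition as a contraindication, and notes that "The mandatory 30-minute monitoring period was removed in 2011".

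**Working it through.** The check is a comparison of text. No power, alpha or precision figure bears on it, and the plan gives no figure to reproduce.

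**Step 1: compare the two rules by type of patient.**

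| Patient with | Section 1.2 | Section 4.2 list |
|---|---|---|
| Right-to-left shunt | Excluded | Excluded (4.2.3) |
| Another known cardiac shunt, stable | Excluded | Not excluded |
| Pulmonary hypertension, pressure above 90 mmHg | Excluded | Excluded (4.2.3) |
| Known pulmonary hypertension, pressure 90 mmHg or lower, stable | Excluded | Not excluded |
| Unstable cardiopulmonary condition | Excluded | Broadly covered by 4.2.1 and 4.2.4 |

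The second and fourth rows are the gap.

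**Step 2: see whether another criterion closes it.**

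- 4.2.1 requires critical illness, instability or intensive care, so a stable patient passes.
- 4.2.2 concerns hypersensitivity to the agents.
- 4.2.4 lists NYHA class IV heart failure, unstable angina, symptomatic arrhythmia and infarction in the previous 14 days. Neither shunt nor pulmonary hypertension is listed.
- 4.2.5 concerns reliable data and meeting the study objectives. It carries a redaction marker, so its text may not be complete. Its purpose and its visible examples (mental illness, drug abuse) do not reach these conditions.
- 4.2.6 and 4.2.7 concern pregnancy or lactation and obesity.

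Nothing visible in 4.2 closes the gap.

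**Step 3: ask whether the Section 1.2 sentence is only loose background.** It first grants that studies show no added risk in pulmonary hypertension and then excludes these patients anyway. That reads as a deliberate precaution. Its undirected reference to cardiac shunts matches the contraindication wording earlier in the section. Section 1.2 is thus consistent with itself, and 4.2.3 is the text that differs. This does not prove which rule was intended.

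**Step 4: look for an effect on the analysis.** The kappas and bootstrap intervals in Section 7.2 use Bosniak readings. Neither they nor the sample-size reasoning in Section 7.1 has an input that depends on this criterion.

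**Step 5: estimate the room to broaden the rule.** Section 7.1 says "The goal of this feasibility study is to enroll a total of 15 subjects", and Section 4.3 counts 20-25 patients under annual screening at UNC. The margin is 20 − 15 = 5 to 25 − 15 = 10 patients, before allowing for refusals, other exclusions or the target of at least 10 subjects with a lesion. Sections 8.3.3 and 8.3.5 refer to affiliate sites and a multi-center study, so the true pool may be larger.

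**The case against.** The strongest reply is that 4.2.3 does not declare other shunts or milder pulmonary hypertension acceptable. It leaves them out. The two texts can be applied together, and an investigator following the whole protocol would exclude these patients. Investigators do the screening, history is taken at screening and again before imaging (Appendix 1), and contrast follows only once the subject has been cleared (Section 6.1). Section 1.2 might also be a general summary that Section 4.2 makes specific. Much of this stands: the texts are not in flat opposition, and screening from Section 4 alone is an inference, though a plausible one. It does not remove the mismatch, because Section 1.2 commits to an exclusion and the clearance step does not mention shunt or pulmonary pressure.

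A reader might go further and infer that the protocol would give contrast to contraindicated patients. The documents do not support that. The contraindication line may be shorthand for prescribing information that Section 1.2 only links to, so they do not show which shunts carry risk.

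Harm after exposure is also limited, by resuscitation cover (Section 6.1), epinephrine near the machine (Section 1.2), nursing monitoring of vital signs (Appendix 1, footnote 6), and stopping the injection with at least 30 minutes of observation (Section 8.5). These measures reduce the consequences of an error but do not settle eligibility.

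**Conclusion.** The mismatch is certain on the face of the text and should be fixed. It is an inconsistency in eligibility and safety wording, of low magnitude. The number of candidates with a non-right-to-left shunt, or with pulmonary hypertension at or below 90 mmHg, is not given and may be zero. Bounding it by the planned enrolment would add no information, so no count is offered. The agreement analyses are unaffected.

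The conclusion assumes that the redaction in 4.2.5 hides nothing about these conditions. Its practical importance also assumes that the Section 4.2 list governs screening. The documents do not show which of the two rules the investigators meant.

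**What to change.** Amend 4.2.3 to read: *Right to left shunt; any other known cardiac shunt; known pulmonary hypertension of any severity; or adult respiratory distress syndrome.* Right-to-left shunt should stay a separate, unqualified item. Placing it inside a phrase about known cardiac shunts could narrow the protection that 4.2.3 now gives. Apply the rule from the comprehensive medical history already scheduled in Appendix 1.

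The cost is one sentence and no new test. A few candidates may become ineligible, which matters somewhat in a counted pool of 20-25 with 15 needed.

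If the investigators intend the narrower rule, correct the Section 1.2 sentence to match 4.2.3 and reconcile it with that section's statement that cardiac shunts are a contraindication, saying why other shunts are acceptable. Eligibility under 4.2.3 would then not change.

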4.2.6 Female patient who is pregnant or lactating

4.2.7 Obesity that limits obtainment of acceptable images

4.3 Subject Recruitment and Screening

Subjects will be recruited from the UNC von Hippel-Lindau Clinical Care Center, under the directorship of [name], NP and [name]. UNC currently has 20-25 patients who undergo annual screening. No specific handouts will be used as the target population is very specific. Principal investigator and sub-investigators will approach patients that meet inclusion and exclusion criteria to determine interest in participation. There are no laboratory tests required. Prior imaging to determine if any lesions are present (as we are targeting at least 10 subjects who have at least one lesion) will be required.

4.4 Early Withdrawal of Subjects

4.4.1 When and How to Withdraw Subjects

The patient may be withdrawn from the study prior to this point if any of the following apply:

- Inter-current illness prevents completion of contrast-enhanced US [REDACTED]
- Unacceptable adverse event(s) prevents completion of CEUS [REDACTED]
- Patient decides to withdraw from the study, OR [REDACTED]
- General or specific changes in the patient's condition render the patient unacceptable for completion of CEUS in the judgment of the investigator.

Subject will be monitored for a minimum of 30 minutes following any possible adverse event related to contrast agent as most reported adverse reactions resolved with clearance of the contrast agent. The Principal Investigator will be notified, and the reason for study removal documented in study documentation sheet.

4.4.2 Data Collection and Follow-up for Withdrawn Subjects

Any subject who is withdrawn from the study will be followed in the immediate post-imaging period and for 72 hours following contrast administration, if contrast agent was administered, for the purpose of detecting any unanticipated adverse effect of contrast administration. If no contrast agent was administered, follow-up will not be required. Since this is a cross-sectional study, and subjects are not being followed longitudinally, subjects that withdraw will also not be followed beyond the 72-hour post-imaging period if complete resolution of any adverse events is noted at 72 hours. If adverse effects are persistent, subjects will continue to be followed until resolution of adverse effects.

5 Study Drug

5.1 Description

5.1.1 Perflutren Lipid Microspheres (Lantheus Medical Imaging) [REDACTED]

The Definity® vial contains components that upon activation yield perflutren lipid microspheres composed of octafluoropropane. Perflutren is a diagnostic drug that is intended to be used for contrast enhancement. The vial contains a clear, colorless, sterile, non-pyrogenic, hypertonic solution which is activated by mechanical agitation with Vialmix®. 

Vialmix® is the activation device used in the preparation of US contrast imaging agents, including Definity®. Prior to activation, each Definity® vial contains 6.52 mg/mL octafluoropropane in the headspace and 0.75 mg lipid blend (0.045 mg DPPA, 0.401 mg DPPC, and 0.304 mg MPEG5000 DPPE), 103.5 mg propylene glycol, 126.2 mg glycerin, 2.34 mg sodium phosphate monobasic monohydrate, 2.16 mg sodium phosphate dibasic heptahydrate and 4.87 mg sodium chloride in water in the clear liquid. Upon activation, each mL of the milky white suspension contains a maximum of 1.2×10^{10} perflutren lipid microspheres with approximately 150 μ L/mL octafluoropropane.

5.1.2 Sulfur hexafluoride lipid microspheres (Bracco Diagnostics Inc)

If Definity is not available, Lumason will be used as a secondary contrast agent.

Lumason (sulfur hexafluoride lipid-type A microspheres) comes in single-patient use kits which contain the following three items:

- 1) one clear glass 10 mL vial containing 25 mg of lyophilized powder lipid-type A, 60.7 mg of sulfur hexafluoride gas and capped with a blue flip-cap
- 2) one prefilled syringe containing 5 mL Sodium Chloride 0.9% Injection, USP (Diluent)
- 3) one Mini-Spike

Each vial is formulated as a 25 mg sterile, pyrogen-free lyophilized powder containing 24.56 mg of polyethylene glycol 4000, 0.19 mg of distearoylphosphatidyl-choline (DSPC), 0.19 mg of dipalmitoylphosphatidylglycerol sodium (DPPG-Na) and 0.04 mg of palmitic acid. The headspace of each vial contains 6.07 mg/mL ($\pm 2\%$) sulfur hexafluoride, SF6, or 60.7 mg per vial.

Each prefilled syringe with 5 mL of diluent 0.9% Sodium Chloride Injection is sterile, nonpyrogenic, preservative free containing 9 mg sodium chloride per mL. Upon reconstitution with 5mL diluent, Lumason is a milky white, homogeneous suspension containing sulfur hexafluoride lipid-type A microspheres.

5.2 Contrast Administration

The contrast agent will be dosed undiluted (0.2-0.3 mL Definity) for up to 7 intravenous injections, depending on the number of lesions (1 injection per kidney and 1 for pancreas in VHL patients, and 1 injection per lesion with remaining injections available per vial if wash-in of the contrast was not captured). The activated undiluted dose of 0.2-0.3 mL will be given as a bolus injection, followed by a total of 5 mL saline flush after the contrast agent is fully injected.

5.3 Method for Assigning Subjects to Treatment Groups

Subjects are not randomized for this study. They will be selected based on prior imaging and meeting the inclusion criteria.

5.4 Preparation and Administration of Study Drug

The contrast agent, Definity (or Lumason), will be dispensed from the UNC Investigational Drug Service (IDS). It will be dispensed in inactivated form to a study team member. The contrast agent will be activated just prior to administration (ideally to be used within 5 minutes of activation). Contrast agent will be activated by nursing staff trained in the activation of Definity (or Lumason) and according to package insert instructions, including use of VialMix®, the device used to activate Definity. Administration will occur IV in coordination with sonography staff trained specifically in contrast ultrasound imaging.

